16.0 DATA AND SAFETY MONITORING PLAN

The Data Safety Monitoring Plan for this study includes the Safety Monitoring Committee (SMC) noted in Section 13.0 above and the safety assessments noted in Section 15.0. As this is an observational study using licensed products consistent with product labeling, external monitoring and a chartered committee with independent representation is not required.

The protocol will be reviewed at least annually and as needed by the Institutional Review Board (IRB). The IRB reviews the study progress and safety information to assess continued acceptability of the risk-benefit ratio for human subjects. Approval of committees as applicable is necessary to continue the study. The study investigators will monitor for adverse events and will refer participants for local medical care if necessary.

17.0 DATA MANAGEMENT/CONFIDENTIALITY

The site principal investigator is responsible to ensure the accuracy, completeness, legibility, and timeliness of the data reported.

Data collection forms will be derived from the eCRF and provided by the Seattle MCTC to record and maintain data for each subject enrolled in the study. All data collection forms should be completed in a neat, legible manner to ensure accurate interpretation of data. Black or blue ink is required to ensure clarity of reproduced copies. When making a change or correction, cross out the original entry with a single line and initial and date the change. Do not erase, overwrite, or use correction fluid or tape on the original.

Data reported in the eCRF should be consistent with all source documents or the discrepancies should be explained.

17.1 Data Management Responsibilities

All data collection forms must be reviewed by the clinical team and data entry staff, who will ensure that they are accurate and complete. Adverse events must be graded, assessed for severity and causality, and reviewed by the site principal investigator or designee. Data collection is the responsibility of the clinical trial staff at the site under the supervision of the site principal investigator. During the study, the investigator must maintain complete and accurate documentation for the study.

The Seattle MCTC will be responsible for data management, quality review, analysis, and reporting of the study data.

17.2 Data Capture Methods

Clinical data (including AE/SAEs, concomitant medications, physical assessments, and reactogenicity data) will be entered into the Seattle MCTC's Clinical Conductor® web-based 21 CFR Part 11-compliant Clinical Trial Management System. Clinical data will primarily be entered directly from the data collection forms.

17.3 Types of Data

Data for this study will include safety, laboratory (clinical and research), and outcome measures (e.g., reactogenicity and immunogenicity).

17.4 Study Records Retention

Records and documents pertaining to the conduct of this study, including eCRFs, data collection forms, consent forms, laboratory test results, and medication inventory records, must be retained by the investigator indefinitely that is the policy of Fred Hutch.

The principal investigators will ensure that this trial is conducted in full conformity with principles of the Belmont Report: Ethical Principles and Guidelines for the Protection of Human Subjects of Research (National Commission for the Protection of Human Subjects of Biomedical and Behavioral Research [April 18, 1979]) and codified in 45 CFR 46, 21 CFR 50 and 21 CFR 56, as applicable. The PI will also ensure conformity with ICH E6 Good Clinical Practice, and applicable federal regulations, guidance, and guidelines for Good Clinical Practice and Clinical Trials with humans.

17.5 Quality Control

The Principal Investigator will provide direct access to all protocol-related source data/source documents, and reports for the purpose of monitoring and auditing and inspection by local and regulatory authorities. The Principal Investigator will ensure all study personnel are appropriately trained and current documentations are maintained on site. All personnel involved in the conduct of this study have completed Human Subjects Protection and ICH GCP Training. The study staff will implement quality control procedures beginning with the data entry system; database quality control checks will be implemented. Any missing data or data anomalies will be updated for clarification and resolution.

18.0 STATISTICAL CONSIDERATIONS

[figure not shown]
18.1 Sample Size and Power for Outcome Measures

The study is designed to demonstrate the safety, tolerability and feasibility of using intradermal BCG as a model for the evaluation of TB drugs. With 5 participants in each arm and a low number of AE/SAEs expected, the study is not powered for direct comparison of the two study groups. Instead, reactogenicity, AEs and SAEs will be presented with descriptive statistics summarizing each group. Interpretation of differences will rely heavily upon clinical judgment. In the rare event that there is a high frequency safety event of at least 25% in one of the groups there will be a 76% chance of observing at least one event and a 37% chance of observing 2 events in the relevant group. All participants are expected to provide safety data.

True event rate (%)	Pr(0/5)	Pr(≥1/5)	Pr(≥2/5)
5	0.77	0.23	0.02

10	0.59	0.41	0.08
15	0.44	0.56	0.16
20	0.33	0.67	0.26
25	0.24	0.76	0.37

It is expected that BCG will be detectable in all skin biopsies provided 4 days after BCG immunization and that the 3 day INH treatment will eliminate detectable BCG in all participants. Therefore, even with only 5 participants per group there will be power to detect a difference in the number of participants with detectable BCG either by qPCR or culture. The plot below shows that a low rate of BCG detection in the treatment arm (<0.05) and a high rate of detection in the control arm (>0.95) there will be >90% power to detect a difference between the groups (Fisher's exact test, two-sided $\alpha=0.05$). Power will be diminished if the actual detection rates are shifted toward 0.5 for either group. It is assumed all participants will contribute data for this objective.

Descriptive statistical analyses will be conducted with the data generated from the Secondary Endpoints. The analyses will generate hypotheses to be tested in future studies.

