10.3 Group Assignment

After the participant meets enrollment criteria, they are randomly assigned by a computer program to 1 of the 2 groups. In both groups, participants will be immunized intradermally with a single dose of 2×10^6 cfu Tice® BCG.

- Group 1 subjects will receive INH dosages on Days 4, 5, and 6.
- Group 2 (control arm) will not receive INH.

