10.6.4 Laboratory Evaluations/Assays

Whole blood samples will be collected via venipuncture for clinical safety laboratory evaluations and BCG response assays. A total of ~730mls (~3 cups) will be drawn for the entire study. At the screening visit (visit 1) and Days 0 (visit 2), 1 (visit 3), 2 (visit 4), 3 (visit 5), 4 (visit 6), 8 ± 1 (visit 7), 15 ± 1 (visit 8), 28 ± 1 (visit 9), 56 ± 2 (visit 10), 84 ± 3 (visit 11), 98 ± 1 (visit 12), 112 ± 1 (visit 14), and 114 ± 1 (visit 15), these standard blood draws will be collected from each participant to perform immunogenicity and humoral assays.

Clinical safety assessments

Blood samples for clinical safety laboratory evaluations (WBC, hemoglobin, platelet count, ALT (SGPT), creatinine) will be collected from each subject prior to administration of Tice® BCG at the screening visit (visit 1). These parameters must meet protocol-defined eligibility criteria to be enrolled and receive Tice® BCG. Additional clinical safety laboratory evaluations may be deemed necessary during the study.

Measuring BCG response

Skin biopsy (via XX)

Skin biopsies will be taken to quantify BCG bacteria. The ID challenge site will be biopsied on Days 3, 8, 15 and 56 (visits 5, 9, 10, and 12) after Tice® BCG administration. A 4mm skin biopsy using the punch method will be taken at the ID challenge site. A local anesthetic injection will be given to numb the site. Gel foam will be used to close the biopsy area. A medically licensed research team member will perform the biopsy.

The number of viable BCG bacteria will be measured on Day 3 from the skin biopsy by 1) quantitative CFU plating, 2) the numbers of genomes of BCG by quantitative real time PCR, and if sufficient material is available, by 3) additional assays may be performed to assess the integrity of the immune system.

Blood samples (via venipuncture)

- Serum will be collected on Days: 0, 1, 2, 3, 4, 8 ± 1 , 15 ± 1 , 28 ± 1 56 ± 2 , and 84 ± 3 , scheduled visits will be collected for inflammatory markers (IL-2, IL-4, IL-5, IL-8, IL-10, INF γ , 1L-12p70, 1L-17A, IL-1, IL-6 and TNF- α levels) using Cytokine BeadArray, and clinical testing for acute phase reactants (ESR and CRP).

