 - Unsolicited AEs/SAEs recorded Days 1-114,
 - Concomitant medications recorded Days 1-114.
- Collection of used dressing/gauze.

Days 4 (clinic visit 6), 5 (clinic visit 7), 6 (clinic visit 8), 8 ± 1 (clinic visit 9), 15 ± 1 (clinic visit 10), and 28 ± 1 (clinic visit 11)

- INH dosing days 4, 5, and 6 only: For the 5 participants assigned to Group 1, they will take INH: oral tablets of either three 100mg tablets (total 300mg) or one 300mg tablet for 3 days post BCG dosing,
- Days 8 ± 1 (clinic visit 9) and 15 ± 1 (clinic visit 10) only: Repeat skin biopsy,
- Assess ID challenge site,
- Review health status and AEs/SAEs that were recorded on the memory aid eCRF device,
- Review concomitant medications,
- Assess for lymphadenopathy if indicated based on review of interim medical history and clinical assessment,

- Targeted physical exam and clinical assessment may be performed if indicated based on review of interim medical history, reactogenicity (as applicable),
- Blood draws via venipuncture for immunogenicity and mycobacteria assays:
 - Day 4: 6.5mls (1.5 tsp),
 - Day 8±1: 74.5mls (5 tablespoons (tbs)),
 - Day 15±1: 56.5mls (4 tbs),
 - Day 28±1: 94.5mls (6 tbs),
- Collect used dressing/gauze,
- Photograph of ID challenge site.

Days 16-114±1

- On-going participant self-evaluations that will be recorded on their memory aid eCRF device for pain, tenderness and drainage. Participants can record their temperature if taken.

Days 56±2 (clinic visit 12) and 84±3 (clinic visit 13)

- Day 56±2 (clinic visit 12) only: Repeat skin biopsy
- Assess ID challenge site (if an abnormal BCG injection site is identified see Abnormal BCG Injection Site Procedures in section 11.3),
- Review health status and AEs/SAEs that were recorded on the memory aid eCRF device,
- Review concomitant medications,
- Assessments for lymphadenopathy if indicated based on review of interim medical history and clinical assessment,
- Targeted general exam and clinical assessment may be performed if indicated based on review of interim medical history, reactogenicity (as applicable),
- Blood draws via venipuncture for immunogenicity and mycobacteria assays:
 - Day 56±2: 94.5mls (6 tbs)
 - Day 84±3: 94.5mls (6 tbs)
- Collect used dressing/gauze,
- Photograph of ID challenge site.

Day 98±1 (clinic visit 14)

- Assess ID challenge site,
- Review health status and AEs/SAEs that were recorded on the memory aid eCRF device,
- Review concomitant medications,

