13.1 Primary Endpoint

- The rate of AE's/SAE's related to Tice® BCG administration reported at any point during the study,
- Summary of the distribution of viable BCG bacteria from intradermal challenge sites at 4 time points (approximately 3 days and 1, 2, and 4 weeks following Tice® BCG administration), as detected by quantitative CFU plating. The distribution will be summarized in terms of its central tendency (mean or GM) and its precision represented by the appropriate 95% confidence interval.

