22.0 APPENDICES

Appendix A: Lab Procedures Table

Procedure	Ship to	Tube	Tube size (vol. capacity)	Tube volume (mL)																	Total			
				Visit:		1	2	3	4	5	6	7	8	9	10	11	12	13	14	15				
				Day:		Screening visit	D0	D1	D2	D3	D4	D5	D6	D8	D15	D28	D56	D84	D98	D100				
				Week:		W0	W0	W0	W0	W0	W0	W0	W1	W2	W4	W8	W12	W14	W16	W16				
				BCG		—	—	—	—	Biopsy	INH	INH	INH	—	—	—	—	—	—	—				
BLOOD COLLECTION																								
Screening or diagnostic assays																								
IGRA	Local Lab	Local Lab	EDTA	5mL	4	—	—	—	—	—	—	—	—	—	—	—	—	—	4	—	4			
Screening HIV test	Local Lab	Local Lab	EDTA	5mL	5	—	—	—	—	—	—	—	—	—	—	—	—	—	—	—	5			
HBsAg/anti-HCV	Local Lab	Local Lab	SST	5mL	5	—	—	—	—	—	—	—	—	—	—	—	—	—	—	—	5			
PPD	?	?	—	Injection	—	—	—	—	—	—	—	—	—	—	—	—	—	X	X	X	0			
Safety labs																								
CBC/Diff/ platelets	Local lab	Local lab	EDTA	5mL	5	—	—	—	—	—	—	—	—	—	—	—	—	—	—	—	5			
Chemistry panel ⁵	Local lab	Local lab	SST	5mL	5	—	—	—	—	—	—	—	—	—	—	—	—	—	—	—	5			
STI Serology																								
Syphilis	Local Lab	Local Lab	SST	5mL	5	—	—	—	—	—	—	—	—	—	—	—	—	—	—	—	5			
Immunogenicity & Mycobacteria assays																								
HLA host genetics	CSR	FHCRC	ACD	8.5mL	—	—	—	—	—	—	—	—	—	—	—	—	—	—	—	—	0			
Cellular assays																								
ICS/ELISPOT / additional tests	CSR	FHCRC	ACD	8.5mL	—	51	—	—	—	—	—	—	51	—	51	51	51	—	—	51	306			
Humoral assays																								
Ab Assays / additional tests	CSR	?	SST	8.5mL	—	17	—	—	—	—	—	—	17	—	17	17	17	—	—	17	102			
Mycobacteria assays																								
BCG PCR	CSR	UW	—		—	—	—	—	—	X	—	—	X	X	X	—	—	—	—	—	0			
BCG Invitro Culture	CSR	CIDR	—	Biopsy	—	—	—	—	—	X	—	—	X	X	X	—	—	—	—	—	0			
Innate Immunity																								
Serum Cytokines	CSR	?	SST	3.5mL	—	3.5	3.5	3.5	3.5	3.5	3.5	3.5	—	—	3.5	3.5	3.5	3.5	3.5	—	35			
Whole Blood Gene Expression	CSR	?	Tempus	3mL	—	3	3	3	3	3	3	3	—	—	3	3	3	3	3	—	30			
STORAGE																								
PBMC	CSR	FHCRC	ACD	8.5mL	—	40	—	—	—	—	—	—	—	—	50	20	20	20	—	—	70	220		
Visit total						29	114.5	6.5	6.5	6.5	6.5	6.5	—	—	74.5	56.5	94.5	94.5	94.5	4	0	4	138	730
56-Day total						29	143.5	150	156.5	163	169.5	—	—	244	300.5	395	489.5	283.5	193	193	197	240.5		
URINE COLLECTION																								
Urinalysis	Local lab	Local lab				X	—	—	—	—	—	—	—	—	—	—	—	—	—	—	—			
Pregnancy test	Local lab	Local lab				X	—	—	—	—	—	—	—	—	—	—	—	—	—	—	—			
Chlamydia/Gonorrhea	Local lab	Local lab				X	—	—	—	—	—	—	—	—	—	—	—	—	—	—	—			

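### Section 18.1 rests its detection comparison on a Day 4 biopsy that is not scheduled, and names neither a post-INH biopsy nor a single readout for the Fisher test

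*Combined protocol and SAP*

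**What the plan says.** Section 18.1 of the combined protocol and SAP expects that BCG will be found in "all skin biopsies provided 4 days after BCG immunization and that the 3 day INH treatment will eliminate detectable BCG" in every participant. It concludes that five participants per group suffice to detect "a difference in the number of participants with detectable BCG either by qPCR or culture". It puts the power above 90% for a two-sided Fisher's exact test at 0.05, when detection is below 0.05 in the INH arm and above 0.95 in the control arm. It assumes that everyone contributes data and warns that power drops as either rate moves toward 0.5. Its last paragraph makes the analysis of the secondary endpoints descriptive.

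The schedule is set elsewhere:

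- **INH.** Section 10.3: "Group 1 subjects will receive INH dosages on Days 4, 5, and 6". Sections 10.4.2 and 11.2 give the same days.
- **Biopsies.** Section 10.6.4: "The ID challenge site will be biopsied on Days 3, 8, 15 and 56". Section 11.2 agrees and lists the last one as "Day 56±2 (clinic visit 12) only: Repeat skin biopsy".
- **Viable count.** Section 10.6.4 also says: "The number of viable BCG bacteria will be measured on Day 3 from the skin biopsy".
- **Endpoints.** Section 13.1 makes CFU plating a primary endpoint, summarised descriptively at four times: "approximately 3 days and 1, 2, and 4 weeks following Tice® BCG administration". Section 13.2 lists the two PCR-based measures as secondary.

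**The concern.** The day named in the power rationale is not a biopsy day, and it falls on the first day of INH dosing. A between-arm test of a three-day INH course needs a biopsy taken after Day 6, with detection rates that apply on that day. Section 18.1 gives neither. It also leaves open which assay defines detection.

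This is the only between-arm test in the plan with a stated power, and it bears directly on whether the challenge model can show a drug effect. With no day and no readout fixed, the comparison reported could be settled after the results are known, in an open-label trial of ten people. The power figure also cannot be checked against any biopsy that will be taken. The 4-week CFU time in 13.1 is a separate mismatch of the same kind, this time in a primary endpoint.

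**Working it through.** **1. Biopsy days against INH dosing.** Dosing days come from 10.3, 10.4.2 and 11.2; biopsy days and windows from 10.6.4 and 11.2.

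| Day | Biopsy scheduled? | INH doses already given in Group 1 | Days since last dose (Day 6) |
|---|---|---|---|
| 3 | yes | 0 of 3 | not applicable |
| 4 (named in 18.1) | no | at most 1 of 3 | not applicable |
| 8±1 | yes | 3 of 3 | 1 to 3 |
| 15±1 | yes | 3 of 3 | 8 to 10 |
| 56±2 | yes | 3 of 3 | 48 to 52 |

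**2. The plan's own power figure.** Inputs from 18.1: 5 v 5, Fisher's exact test, two-sided 0.05, control rate 0.95, INH rate 0.05. The test rejects only at 5/5 v 0/5 (p = 0.0079), at 5/5 v 1/5 and 4/5 v 0/5 (both p = 0.0476), and at the mirror images.

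- P(5/5 in control) = 0.95^5 = 0.7738; P(4/5 in control) = 5 × 0.05 × 0.95^4 = 0.2036.
- P(0/5 on INH) = 0.95^5 = 0.7738; P(1/5 on INH) = 5 × 0.05 × 0.95^4 = 0.2036.
- Power = 0.7738 × 0.7738 + 0.7738 × 0.2036 + 0.2036 × 0.7738 = 0.5987 + 0.1576 + 0.1576 = 0.914 (the mirror tables add a negligible amount).

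The statement of more than 90% is correct at those rates.

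**3. Could the nearest biopsy, Day 3, carry the test?** No. Before INH, randomised arms share one detection rate. At a common rate of 0.5 the rejection probability is [2 × 1 + 4 × 5] / 1024 = 22/1024 = 2.1%, which is the maximum over all common rates. At 0.95 it is 0.00005. Day 3 can serve only as a baseline.

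**4. Sensitivity to the rates on the chosen day.** The documents give no detection rates for Day 8, 15 or 56. Every pair below except the first is assumed; the method is that of step 2.

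| Control | INH | Power |
|---|---|---|
| 0.95 | 0.05 | 91.4% (rates in 18.1) |
| 0.93 | 0.05 | 88.3% |
| 0.90 | 0.05 | 83.1% |
| 0.90 | 0.10 | 73.6% |
| 0.80 | 0.05 | 63.7% |

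A fall of two points in control detection is enough to take power below 90%, so the day to which the rates apply matters.

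**5. Readout.** Culture is primary (13.1). The PCR measures are secondary (13.2), and 18.1 analyses secondary endpoints descriptively. Offering qPCR as an alternative basis for the powered test conflicts with that.

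**6. The 4-week CFU time.** Day 56 / 7 = week 8. A Day 28±1 visit exists, but 11.2 puts no biopsy on it. The last CFU time in 13.1 therefore has no biopsy behind it.

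**The case against.** The best defence is that 18.1 conditions its power on detection rates, not on Day 4. On that reading, the 4-day phrase only says that BCG will be detectable early, probably a slip for Day 3, and the comparison would naturally use a later biopsy. This is fair, and it disposes of one tempting inference: that the test is planned on Day 4 or Day 3 and so has almost no power. The documents do not say so, and post-INH biopsies exist. What stands is that the control rate that matters is the one on the post-INH day, and 18.1 ties its rates to no such day.

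Looser phrases, such as the Dose entry in the synopsis, could be read as INH on the three days straight after BCG. Sections 10.3, 10.4.2 and 11.2 fix Days 4 to 6, and either reading leaves no Day 4 biopsy.

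Other stronger readings also go too far:

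- A reader might count three post-INH biopsies by two assays as six competing tests. Because 18.1 makes secondary endpoints descriptive, that is only the most open reading, and the plan does not establish it.
- A reader might infer that residual nucleic acid would ruin a qPCR comparison. Section 5.3.3 makes its viability remark about 16S rRNA, the listed endpoint is 16S rDNA PCR, and no post-INH PCR rates are given.
- A reader might take 10.6.4 to mean that culture is done on Day 3 only. The same section introduces the biopsies on all four days as a means of quantifying BCG, so the Day 3 sentence may simply be incomplete.
- The culture row of Appendix A settles nothing here, because its columns do not line up in the text available for this review.

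It is also true that this is a ten-person feasibility study, that the CFU endpoint is descriptive, and that no stated decision depends on the Fisher test. That limits the weight of the point, not its correctness.

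**Conclusion.** The time point in 18.1 is wrong as written. There is no Day 4 biopsy, the Day 3 biopsy precedes INH, and no post-INH biopsy is named for the comparison. The power calculation itself is right: 91.4% at 0.95 v 0.05. That figure carries over to a post-INH biopsy only if those rates hold on that day; over the nearby rates assumed above it runs from 88.3% down to 63.7%. These lower values show sensitivity and do not predict what will be seen. The choice between qPCR and culture conflicts with the plan's own ranking of endpoints. Separately, the 4-week CFU time in 13.1 does not match the schedule, whose last biopsy is at week 8. The conclusion rests on INH being given on Days 4 to 6, as 10.3, 10.4.2 and 11.2 all state.

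**What to change.** In 18.1:

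- Replace the 4-day reference with the Day 3 biopsy, labelled as the pre-INH baseline in both arms.
- Name one post-INH biopsy for the Fisher test: Day 8±1, or Day 15±1 if Day 8 tissue is reserved for immunology. The legend of Appendix B may indicate such a reservation, although X is also that table's ordinary tick.
- Name culture as the single inferential readout, with qPCR descriptive.
- State the detection rate assumed in each arm on that day, and restate the power if the rates differ from 0.95 and 0.05.

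In 13.1, change 4 weeks to 8 weeks (Day 56). In 10.6.4, make clear that CFU plating is done on the named post-INH biopsy and not only on Day 3.

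The cost is wording only: no added visit, biopsy or participant. The exception would be a Day 8 punch that had to be shared between culture and immunology; using Day 15 avoids it.

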18.2 Randomization

The participants assignment to either Group 1 and 2 will be computer generated.

18.3 Ethnic and Gender Distribution Chart

The target population reflects the Seattle King County community. Projected Target Accrual

ETHNIC AND GENDER DISTRIBUTION CHART

TARGETED / PLANNED ENROLLMENT: Number of Subjects			
Ethnic Category	Sex / Gender		
	Females	Males	Total
Hispanic or Latino	0	0	0

Not Hispanic or Latino	5	5	10
Ethnic Category Total of All Subjects*	5	5	10
Racial Categories			
American Indian / Alaska Native	0	0	0
Asian	1	1	2
Native Hawaiian or Other Pacific Islander	0	0	0
Black or African American	0	0	0
White	4	4	8
More Than One Race	0	0	0
Racial Categories: Total of All Subjects*	5	5	10

19.0 ETHICS/PROTECTION OF HUMAN SUBJECTS

19.1 Institutional Review Board

The participating institution will provide for the review and approval of this protocol and the associated informed consent documents and recruitment material to the Fred Hutch IRB, registered with OHRP. Any amendments to the protocol or consent materials will also be IRB approved before they are placed into use.

19.2 Informed Consent Process

Informed consent is a process that is initiated prior to the individual's agreeing to participate in the study and continuing throughout the individual's study participation. Extensive discussion of risks and possible benefits of participation in this study will be provided to the subjects and their families. Consent forms describing in detail the study procedures and risks are given to the subject and written documentation of informed consent is required prior to enrolling in the study. Consent forms will be IRB approved and the subject will be asked to read and review the document. Upon reviewing the document, the investigator will explain the research study to the subject and answer any questions that may arise. The subjects will sign the informed consent document prior to being enrolled in the study. The subjects should have the opportunity to discuss the study with their surrogates or think about it prior to agreeing to participate. The subjects may withdraw consent at any time throughout the course of the study. A copy of the informed consent document will be given to the subjects for their records. The rights and welfare of the subjects will be protected by emphasizing to them that their medical care will not be adversely affected if they decline to participate in this study.

